4.6. Safety Analyses

Baseline for AACQ safety analyses refers to all adverse events that started before first dose of donanemab. Postbaseline for safety reviews includes data obtained during treatment period plus safety follow-up period.

4.6.1. Extent of exposure

Descriptive statistics, like mean, median, interquartile range, and range will be used to summarize the number of infusions per treatment arm. In each dosing regimen, the number and percentage of subjects with the number of infusions will be reported as well.

4.6.2. Adverse events

Treatment-emergent adverse events (TEAEs) in the safety analysis set will be defined as events that first occurred or worsened on or after the day of first donanemab dose. The MedDRA lower-level term (LLT) will be used in the treatment-emergent computation and the LLT of each baseline event will be used as baseline. Should there be insufficient data for AE start date, stop date, and time to make this comparison, imputation method will be used for partially missing dates. Missing dates of adverse events or concomitant medicine will be handled such that incomplete start dates of the current disease episode will be imputed in a manner resulting in the earliest possible onset. In order to calculate the durations in years from the onset of AD symptoms from the diagnosis of AD, the start date of the onset of AD symptoms and AD diagnosis will be defined in the following manner:

- The date itself if it is available as day, month and year.
- The date of the first day of the month, if month and year are available but the day is missing. For example, ??FEB2022 will be completed as 01FEB2022.
- The date of the first day of the year, if year is available but day and month are missing. For example, ?????2022 will be completed as 01JAN2022.

• If the date is completely missing, the duration will not be calculated and will form part of a "Missing" category.

The imputed values of incomplete data will not be presented in the patient data listings and will only be used to derive the durations described above.

An overview of AEs by treatment arm, including the number and percentage of patients who died, experienced serious adverse events (SAEs), discontinuations from study treatment due to an AE and TEAE will be displayed. Besides descriptive statistics, odds ratios with any alternative dosing regimen as the numerator and standard dosing regimen as the denominator, and *p*-values derived from Fisher's exact test may be reported for AE overview.

Summaries of AEs by decreasing frequency of preferred term (PT) within system organ class (SOC) will be provided per treatment arm for the following:

- TEAEs
- TEAE with maximum severity
- TEAEs occurring in greater than or equal to 2% of patients by PT
- Serious adverse events
- Adverse events reported as reason for study treatment discontinuation
- Adverse events reported as reason for study discontinuation

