4.3. Primary Endpoint Analysis

4.3.1. **Definition of endpoint(s)**

The primary endpoint will be the occurrence of ARIA-E as diagnosed by the scheduled or unscheduled MRIs or reported as treatment-emergent cluster up to and including Visit 12 (Week 24). The scheduled MRIs for the primary endpoint occur at weeks 4, 12, and 24.

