6.3. Appendix 3: Concomitant Therapy

Prior medications are defined as those that stop before randomization (the day prior to the first administration of study drug). Concomitant medications are defined as prior medications being

taken in any time during the treatment period and follow-up period. A summary of concomitant medications that were used will be presented through frequencies and percentages for safety analysis set. If the start or stop dates of therapies are missing or partial to the degree that determination cannot be made of whether the therapy is prior or concomitant, the therapy will be deemed concomitant.

Medications will be coded using the World Health Organization (WHO) drug dictionary.

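### SAP 4.6.2 sends incomplete adverse-event start dates to the earliest possible onset with no floor at first dose, which can only lower TEAE counts, and then contradicts its own use of imputed dates

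*SAP*

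**What the plan says.** SAP 4.6.2 defines a TEAE as "events that first occurred or worsened on or after the day of first donanemab dose". SAP 4.6 fixes the other side of the line: "Baseline for AACQ safety analyses refers to all adverse events that started before first dose of donanemab". In 4.6.2 the MedDRA lower-level term (LLT) of each such event is then the baseline for the treatment-emergent computation.

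Where date information is too thin for that comparison, 4.6.2 says an "imputation method will be used for partially missing dates". The next sentence, whose subject is missing dates of adverse events or concomitant medicine, gives the direction: "incomplete start dates of the current disease episode will be imputed in a manner resulting in the earliest possible onset".

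The section then spells out mechanics for two other dates, onset of Alzheimer's disease (AD) symptoms and AD diagnosis. For a missing day: "For example, ??FEB2022 will be completed as 01FEB2022". For a missing day and month: "The date of the first day of the year, if year is available but day and month are missing". It closes by saying that imputed values stay out of the listings and serve solely to derive those durations.

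SAP Appendix 3 (6.3) covers medications whose dates do not allow them to be classed as prior or concomitant: "the therapy will be deemed concomitant".

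**The concern.** Earliest-date imputation is a sensible convention for disease duration. For treatment emergence it resolves every doubt toward onset before treatment, and a safety analysis normally resolves that doubt the other way. An event moved before first dose is lost from the TEAE tables. It also becomes the baseline for its LLT, so a later event under the same term counts only if it worsened.

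The losses would fall just after the first infusion. In this trial the arms differ in dosing during the first weeks, and TEAE summaries by arm are part of the comparison. The hypersensitivity and infusion-reaction categories in SAP 4.6.7 are also built from TEAEs.

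**Working it through.** The plan states no figure on this point, so there is none to reproduce. Its sample size, power and false-positive rate do not depend on this rule.

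**Direction.** The earliest possible date is never later than the true date. Imputation can therefore move an event from on-or-after first dose to before it, but never the reverse.

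**Illustration (dates invented).** First dose is 15 March 2023, true onset 20 March 2023, and the start is recorded as month and year only. The earliest possible onset is 1 March, so the event becomes baseline. With only the year known, it becomes 1 January 2023.

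**Nothing else in the plan stops this.** Adverse events are collected from consent (Schedule of Activities), and screening runs up to 49 days, so pre-dose dates are valid in the database. The dose date and time are recorded (Protocol 6.5), so a first-dose floor could be programmed.

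**First-dose dates exposed**, assuming they are uniform over a 365-day year:
- Day missing, onset in the first-dose month: every date except the 1st of a month, (365 − 12)/365 = 96.7%.
- Day and month missing, onset in the first-dose year: every date except 1 January, 364/365 = 99.7%.

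**Share of partly dated post-dose events moved before dosing**, assuming onset is also uniform over days 0 to w (N = w + 1 days). For each first-dose date, count the post-dose days left in that month (or year), capped at N. Count zero if dosing fell on the 1st (or on 1 January). Sum over the 365 dates and divide by 365 × N.

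For a missing day and w of 84 or more, the sum is 7 × 465 (31-day months) + 4 × 435 (30-day months) + 378 (February) = 5,373. For w = 28 the cap applies once in each 31-day month, giving 7 × 464 + 4 × 435 + 378 = 5,366.

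| Onset window | Day missing | Day and month missing |
|---|---|---|
| Days 0–28 | 5,366/(365 × 29) = 50.7% | 10,150/(365 × 29) = 95.9% |
| Days 0–84 | 5,373/(365 × 85) = 17.3% | 27,370/(365 × 85) = 88.2% |
| Days 0–168 | 5,373/(365 × 169) = 8.7% | 47,320/(365 × 169) = 76.7% |
| Days 0–532 | 5,373/(365 × 533) = 2.8% | 66,430/(365 × 533) = 34.1% |

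**Absolute size.** The documents give no rate of partial dates. If 1–3% of post-dose events had only the day missing (an assumption), the loss would be 0.01 × 50.7% to 0.03 × 50.7%, or 0.5–1.5%, of events in days 0–28. To Week 76 it would be 0.01 × 2.8% to 0.03 × 2.8%, or 0.03–0.08%.

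**Primary endpoint.** SAP 4.3.1 counts ARIA-E found on any scheduled or unscheduled MRI, or "reported as treatment-emergent cluster up to and including Visit 12 (Week 24"). Only a case captured solely through the adverse-event route, with a partial date, is exposed. Expected cases in a standard arm: 800/4 × 0.9 = 180 participants, and 180 × 18.5% = 33.3. Assume 0–20% of cases are adverse-event-only and 2–10% of those are partly dated; neither range comes from the documents. The upper bound is 33.3 × 0.20 × 0.10 × 8.7% = 0.06 cases with the day missing, or 33.3 × 0.20 × 0.10 × 76.7% = 0.51 with day and month missing. The lower bound is 0.

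**The case against.** The best defence is the closing sentence of the date rules in 4.6.2. If imputed values serve only AD durations, no adverse event is moved. The first-of-month and first-of-year mechanics are also written only for AD dates; for adverse events they are inferred from the earliest-onset wording. This stands as a bar to saying that events will certainly drop out. It does not clear the plan. The same section invokes imputation for the treatment-emergent comparison, and if the closing sentence governs, partly dated events have no rule at all.

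Several further points limit the size:
- Infusion reactions are tied to a recorded infusion and have a dedicated form, so a missing day is least likely there.
- Protocol 8.3.3.1 places serious ARIA after the first to third standard infusions. The second and third are at Weeks 4 and 8, normally in a later calendar month, where a missing day does no harm.
- Visits every two weeks to Week 16 make year-only dates unlikely.
- Events that worsen after dosing still qualify as TEAEs, and 4.6.2 lists serious events and discontinuations separately without restricting them to TEAEs.
- Some partly dated events in the first-dose month truly began before dosing.
- The rule is the same in every arm. Losses could differ only if early event rates or date completeness differ, which the documents do not show.

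The contrast with medications is less clean than it looks. Section 4.6.2 puts concomitant medicine under the earliest-onset rule as well, and Appendix 3 defines prior use by the stop date. The two places still need to be aligned.

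A reader might infer that the rule removes ARIA-E cases from the primary endpoint. The documents do not support that as a material effect. MRI-detected ARIA-E counts whatever its adverse-event date, ARIA-E reporting is itself triggered by MRI (Protocol 8.3.3.1), and ARIA-E on the screening MRI is an exclusion.

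**Conclusion.** The concern holds as a defect in the TEAE derivation. SAP 4.6.2 either applies a rule that can only lower TEAE counts or, through its closing restriction, leaves partly dated adverse events without a rule. Both readings call for the same repair.

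Under the literal reading the effect is concentrated in the first-dose month, or in the first-dose year when the month is also unknown. Its absolute size is probably small but cannot be fixed, because it rests on an unstated partial-date rate and on the uniform-date assumptions above. The effect on the primary endpoint is near nil. A bias between arms is possible but not demonstrated.

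**What to change.** - State one rule for adverse events: a partly dated event is treatment-emergent unless the known date parts or the stop date show onset before first dose. When it is treatment-emergent under this rule and onset in the first-dose month or year is possible, set onset to the first-dose date.
- Confine the earliest-date rule, and the sentence restricting imputed values to durations, to AD symptom-onset and AD diagnosis dates.
- Align the concomitant-medicine wording in 4.6.2 with Appendix 3.

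The cost is a few SAP sentences and minor derivation code. Sample size, power and false-positive rate do not change. The downside is that a few events that truly began before dosing may be counted as TEAEs, so TEAE counts may look slightly less favourable. Under this rule no post-dose event is moved before dosing by imputation.

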4.6.4. Vital signs and other physical findings

Vital sign measurements and weight will be analyzed using continuous data (change from baseline) and categorical data (proportion of potentially clinically significant changes) using all safety data set. Vital sign measurements include systolic and diastolic blood pressure and pulse (collected in sitting position), orthostatic diastolic and orthostatic systolic blood pressures and orthostatic pulse (measurement after at least 5 minutes in the supine position minus that after at least 3 minutes in the standing position), and temperature.

If there are multiple records of vital sign or weight measurements at baseline or postbaseline visit, the last record will be used. For the analysis of vital signs and weights, summary statistics like mean and SD per treatment arm will be presented for observed values at baseline and for change from baseline results at each scheduled postbaseline visit. The application of ANCOVA will be used to assess whether 4 treatment means of a post-baseline vital sign or weight are different or not after adjusting baseline vital sign or weight.

The incidence of treatment-emergent abnormal high or low vital signs and weight will be presented using safety analysis set. Treatment-emergent vital sign evaluations are defined for evaluations collected after the initiation of donanemab. Abnormal criteria for post-baseline vital signs and weight are presented in Table 4.1. Any vital sign or weight meeting the criteria will be considered abnormal. The proportion of patients with treatment-emergent abnormal high or low vital signs and weight by treatment arm will be provided regardless of their baseline results. And an odds ratio of having treatment-emergent abnormal high or low vital signs or weight in each alternative dosing regimen compared to the standard dosing regimen can be computed. A *p*-value generated from Fisher's exact test will confirm if proportions of treatment-emergent abnormal high or low vital signs or weight are statistically different between the alternative and standard treatment arms.

Summary and analyses of change from baseline in weight will be provided. The proportion of patients with a weight gain or loss of greater than or equal to 7 percent of baseline body weight will be summarized in each treatment arm using safety analysis set.

Table 4.1. Potentially Clinically Significant Changes in Vital Sign and Weight.

Vital Sign Parameter (Unit)	Postbaseline Low Criteria	Postbaseline High Criteria
vitai sign i arametei (Unit)	i ostbasenne Low Citteria	i ostbasenne mgn Criteria

Sitting systolic blood pressure	Absolute value ≤90 and ≥20 decrease	Absolute value ≥160 and ≥20 increase
(mmHg)	from baseline	from baseline
Sitting diastolic blood pressure	Absolute value ≤50 and ≥10 decrease	Absolute value ≥100 and ≥10 increase
(mmHg)	from baseline	from baseline
Sitting pulse (bpm)	Absolute value <50 and ≥15 decrease	Absolute value >100 and ≥15 increase
	from baseline	from baseline
Weight	≥7% decrease	≥7% increase
Vital Sign Parameter (Unit)	Postbaseline Criteria for Abnormality	y
Vital Sign Parameter (Unit) Orthostatic systolic blood	Postbaseline Criteria for Abnormality ≥20 mmHg decrease in systolic blood p	
Orthostatic systolic blood	≥20 mmHg decrease in systolic blood p	ressure (supine to standing)
Orthostatic systolic blood pressure (mmHg)	≥20 mmHg decrease in systolic blood p (i.e., standing minus supine ≤–20)	ressure (supine to standing) pressure (supine to standing)
Orthostatic systolic blood pressure (mmHg) Orthostatic diastolic blood	≥20 mmHg decrease in systolic blood p (i.e., standing minus supine ≤-20) ≥10 mmHg decrease in diastolic blood p	ressure (supine to standing) pressure (supine to standing) Ig)
Orthostatic systolic blood pressure (mmHg) Orthostatic diastolic blood pressure (mmHg)	≥20 mmHg decrease in systolic blood p (i.e., standing minus supine ≤-20) ≥10 mmHg decrease in diastolic blood p (i.e., standing minus supine ≤ -10 mm F	ressure (supine to standing) pressure (supine to standing) Ig) (i.e., standing minus supine ≥30)

Abbreviation: bpm = beats per minute; mmHg = millimeters of mercury.

4.6.5. Columbia-Suicide Severity Rating Scale

Suicide-related thoughts and behaviors occurring through the end of the study which includes safety follow-up period will be summarized based on the Columbia-Suicide Severity Rating Scale (C-SSRS). The composite measure is determined at each assessment by the "yes" or "no" responses in C-SSRS categories by study patient.

- Category 1 Wish to be Dead
- Category 2 Non-specific Active Suicidal Thoughts
- Category 3 Active Suicidal Ideation with Any Methods (Not Plan) without Intent to Act
- Category 4 Active Suicidal Ideation with Some Intent to Act, without Specific Plan
- Category 5 Active Suicidal Ideation with Specific Plan and Intent
- Category 6 Preparatory Acts or Behavior
- Category 7 Aborted Attempt
- Category 8 Interrupted Attempt
- Category 9 Actual Attempt (non-fatal)
- Category 10 Completed Suicide

Self-injurious behavior without suicidal intent is also a C-SSRS outcome (although not suicide-related) and has a binary response (yes/no).

Composite endpoints based on the above categories are defined below.

- Suicidal ideation: A "yes" answer at any time during treatment to any one of the five suicidal ideation questions (Categories 1-5) on the C-SSRS.
- Suicidal behavior: A "yes" answer at any time during treatment to any one of the five suicidal behavior questions (Categories 6-10) on the C-SSRS.
- Suicidal ideation or behavior: A "yes" answer at any time during treatment to any one of the ten suicidal ideation and behavior questions (Categories 1-10) on the C-SSRS.

Patients who discontinued from the study with no postbaseline C-SSRS value will be considered unevaluable for analyses of suicide-related events. Only evaluable patients will be considered in the analyses. The proportion of patients with suicidal ideation, suicidal behavior, or either suicidal ideation or behavior per treatment arm will be tabulated through safety analysis set.

Number of patients with suicide-related treatment-emergent events based on the C-SSRS may be reported for safety analysis set:

- Treatment-emergent suicidal ideation compared to recent history
- Treatment-emergent serious suicidal ideation compared to recent history
- Emergence of serious suicidal ideation compared to recent history
- Improvement in suicidal ideation at endpoint compared to baseline

Emergence of suicidal behavior compared to all prior history "Treatment emergence" is used for outcomes that include events that first emerge or worsen. "Emergence" is used for outcomes that include events that first emerge.

In case the following suicide-related events occur, the counts and percentages of patients of the event by treatment arm will be summarized from safety analysis set:

- died by suicide
- nonfatal suicide attempt
- interrupted attempt
- aborted attempt
- preparatory acts or behavior
- active suicidal ideation with specific plan and intent
- active suicidal ideation with some intent to act without specific plan
- active suicidal ideation with any methods (no plan) without intent to act
- nonspecific active suicidal thoughts
- wish to be dead, and
- nonsuicidal, self-injurious behavior

4.6.6. Amyloid-Related Imaging Abnormalities (ARIA)

ARIA incidence was discussed in Section 4.3, Section 4.4.1, and Section 4.4.3. Severity of ARIA events was covered in Section 4.4.3.

Unless otherwise specified, safety analyses of ARIA events are based on centrally read MRI findings from both scheduled and unscheduled visits. Where applicable, ARIA-E summaries will be presented for symptomatic and asymptomatic ARIA-E. ARIA-H summaries will be presented by ARIA-H microhemorrhage and ARIA-H superficial siderosis. Macrohaemorrhage will be described separately and will not be included in the ARIA-H category.

An overview of ARIA incidence by treatment arm from safety analysis set will be presented using frequency and percentage of patients with any ARIA (ARIA-E or ARIA-H), ARIA-E, and ARIA-H as defined by safety MRIs or treatment-emergent AE clusters. The proportion of the patients with serious adverse events of ARIA, ARIA-E, and ARIA-H with or without ARIA-E will be summarized via treatment arm. The frequency and percentage of ARIA-E will be further

broken out by asymptomatic vs. symptomatic and by APOE genotype. The frequency and percentage of subjects with ARIA-H microhemorrhage, ARIA-H superficial siderosis, and macrohemorrhage will be further broken out by APOE genotype. A sensitivity analysis of overview of ARIA incidence will be performed utilizing per-protocol analysis set.

A severity shift table of ARIA-E, ARIA-H microhemorrhage, and ARIA-H superficial siderosis severity from baseline to Week 76 by visit and by treatment arm will be presented.

To investigate the onset of the first ARIA-E or ARIA-H event among different dosing regimens, Kaplan-Meier plots will be presented using safety analysis set. Besides Kaplan-Meier plots, histograms of the onset of the first ARIA-E or ARIA-H based on safety MRI may be provided to visually inspect timing of the first ARIA event across treatment arms.

From safety analysis set, mean and median duration before the resolution of ARIA-E or the mean and median duration of ongoing ARIA-E events for each dosing regimen will be derived.

